6.0 REGULATORY, ETHICAL, AND STUDY OVERSIGHT CONSIDERATIONS

6.1 Informed Consent Process

Informed consent is a process that is initiated prior to the individual's agreeing to participate in the study and continues throughout the individual's study participation. All patients referred by the general physician or psychiatrist will undergo an extensive consultation with a brain stimulation psychiatrist at each study site. The brain stimulation psychiatrist will determine eligibility for referral to the randomized control trial. They will explain the research study to the patient and answer any questions that may arise. A verbal explanation will be provided in terms suited to the patient's comprehension of the purposes, procedures, and potential risks of the study and of their rights as research participants. Patients who are referred to the trial will be

seen for eligibility screening by qualified research personnel. Research personnel will also explain the trial in detail prior to obtaining consent. Consent forms describing in detail the study intervention, study procedures, and risks are given to the participant and written documentation of informed consent is required prior to completing the initial screening visit and starting the study intervention. Once consent is obtained according to IRB and GCP/Tri-Council guidelines, the research personnel will confirm inclusion/exclusion criteria is met before proceeding with baseline testing. Patients will be informed that they can withdraw participation at any point during the study. A copy of the informed consent document will be given to the participants for their records. The informed consent process will be conducted and documented in the source document (including the date), and the form signed, before the participant undergoes any study-specific procedures. The rights and welfare of the participants will be protected by emphasizing to them that the quality of their medical care will not be adversely affected if they decline to participate in this study.

6.2 Confidentiality

Procedures designed to maintain confidentiality include: (1) formal training sessions for all research staff emphasizing the importance of confidentiality; (2) specific procedures developed to protect subjects' confidentiality, and (3) formal mechanisms limiting access to information that can link data to individual subjects. Data forms that include identifying information will be kept in locked cabinets. Only the unique ID number, assigned by the research coordinator at the time of initial contact will represent subjects during data entry, data transfer, data analysis, or other file management procedures. To facilitate tracking, a password-protected computer file will be maintained containing the identity of subjects, their ID numbers, and information about how they can be reached. This file, however, will contain no clinical data. Only members of the investigative group will have access to secured files or to master lists for subject code numbers and will be well-informed regarding the protection of patients' rights to confidentiality. Identities of participants will not be revealed in the publication or presentation of any results from this project. Such procedures will follow the Institutional Review Board (IRB) policies at all study sites.

6.3 Publication and Data Sharing Policy

This study will be conducted in accordance with the following publication and data sharing policies and regulations:

NIH Public Access Policy, which ensures that the public has access to the published results of NIH funded research. It requires scientists to submit final peer-reviewed journal manuscripts that arise from NIH funds to the digital archive PubMed Central upon acceptance for publication.

This study will comply with the NIH Policy on the Dissemination of NIH-Funded Clinical Trial Information and FDA Clinical Trials Registration and Results Information Submission rule. As such, this trial will be registered at ClinicalTrials.gov, and results information from this trial will be submitted to ClinicalTrials.gov. In addition, every attempt will be made to publish results in peer-reviewed journals.

Data from this study may be submitted to the National Institute of Mental Health Data Archive (NDA). NDA is a data repository run by the National Institute of Mental Health (NIMH) that allows researchers studying mental illness to collect and share deidentified information with each other. During and after the study, the researchers will send deidentified information collected from participants to NDA.

6.4 Quality Assurance: Data Management Procedures

Each clinical site will perform internal quality management of study conduct, data collection, documentation and completion. Quality control (QC) procedures will be implemented beginning with the data entry system and data QC checks that will be run on the database will be generated. Any missing data or data anomalies will be communicated to the site(s) for clarification/resolution.

CAMH has established a service agreement with an academic clinical research organization, the Applied Health Research Centre (AHRC) at St. Michael's Hospital (SMH) in Toronto, Canada. [name], Head of Biostatistics at AHRC, will serve as study statistician consulting on the design and implementation of our statistical plan via a collaboration agreement.

The purpose of the service agreement is to engage the services of AHRC to provide a safe and secure electronic data management system, which will facilitate the conduct of this large scale, multi-centre trial. This system is PHIPA compliant and is designed to meet the regulatory requirements of organizations such as Health Canada and the FDA. We will use software called Medidata RAVE (www.mdsol.com) to create the web-based electronic case report forms (eCRF). All study data will be securely stored on local servers at SMH throughout the duration of the study and for up to 10 years after the study is complete. All study subjects will be identified in the database by a unique study ID number. Linkages between the patient name/contact information and the study ID will be retained at the local site and not shared with the study data coordination centre (DCC) or outside the institution. At the end of the study (after all analyses are complete) the DCC will transfer all study datasets over to the study PI (and site data to site PIs.) Data will only be accessible by authorized study site personnel and authorized central DCC personnel. Authorized personnel receive a username and password which is unique, and database access is controlled by the DCC in collaboration with the PI. The SMH data centre infrastructure has several features in place to enhance the security of data, prevent data loss and mitigate downtime. These include: duplicate internet service providers (ISPs), mirror database, web and application servers, replicated firewalls, two data centres (environmentally controlled and monitored with fire retardant systems.) Several additional measures are in place for the protection of study data. These include training of all staff on the use of personal health information in research (Personal Health Information Protection Act), the ongoing creation of a set of SOPs regarding roles, access to the system, security, privacy, data management, and others. Furthermore, with the support of the Privacy Officer of SMH, the RAVE system (hardware, software, and systems and processes) successfully completed a comprehensive Threat Risk Assessment (TRA) conducted by an independent third party consulting firm, to demonstrate that appropriate technical security is in place, and that systems/processes meet current standards.

Study data can only be accessed via application by authorized users or by dedicated database administrators through the database end.

7.0 ADDITIONAL CONSIDERATIONS

7.1.1 Study Initiation Timeline

In order to ensure that the protocol milestones are met in a timely manner, the initial funded period of six months (Aug 1, 17 – Feb 1, 18) has been designated for trial set-up and organization. This includes the following:

- 1) Obtaining regulatory approvals from FDA in the United States and Health Canada in Canada
- 2) Obtaining institutional review board approvals at CAMH and UTSW
- 3) Preparation of electronic case report forms to facilitate data management and data collection
- 4) Building study SOPs and Manual of Procedures (MOPs)
- 5) Conducting the hiring process at CAMH and UTSW.
- 6) Receipt, certification and installation of the MST devices as per each institution's procedures
- 7) [name] has a scheduled visit to UTSW in January 2018 for a review of the facility and to meet the ECT service staff
- 8) Investigators' Meeting planned for January 2018 at CAMH to conduct training, review study procedures and ensure standardization across both sites
- 9) CAMH to send staff to UTSW for further neurophysiology training later in January, as part of the neurophysiology lab set-up
- 10) Site initiation visits are planned for February/March 2018
- 11) Addition of UCSD as a third site in March 2022
- 12) Proposed study start at UCSD in Summer 2022

7.1.2 Study Timeline

The study timeline is as follows:

Duration of Project Funding: August 1, 2017 – April 30, 2022

Duration of enrollment: March 1, 2018 – March 30, 2022

Projected annual enrollment at CAMH and UTSW:

August 1, 2017 – April 30, 2018 (Year 1): First six months are devoted to study start-up: August 1, 2017 – January 31, 2018. By end of year 1 (April 30, 2018), 8% of total target recruitment is expected.

May 1, 2018 – April 30, 2019 (Year 2): Enrollment to continue with 2 -3 people enrolled per site per month. By end of year 2 (April 30, 2019), 26% of total target recruitment is expected.

May 1, 2019 – April 30, 2020 (Year 3): Enrollment to continue with 3 people enrolled per site per month. By end of year 3 (April 30, 2020), 52% of total target recruitment is expected.

May 1, 2020 – April 30, 2021 (Year 4): Enrollment to continue with 3 people enrolled per site per month. By end of year 4 (April 30, 2021), 77% of total target recruitment is expected.

May 1, 2021 – April 30, 2022 (Year 5): Enrollment to continue with 3 people enrolled per site per month. By March 2022, 100% of total target recruitment is expected.

Data analysis/queries: This will be ongoing through the trial from Year 2 to Year 5.

8.0 REMOTE AND MODIFIED STUDY DELIVERY (COVID-19)

This section of the protocol details the CREST-MST study procedures and how they will be modified, including remote delivery of study assessments. This section will serve as a guide for study and site specific operating procedures. Participants and research personnel will wear appropriate PPE based on institutional guidelines at the time during any procedures that are completed in person.

8.1 Informed Consent Process

Informed consent will be collected according to institutional guidelines to ensure participant and study team safety. At CAMH, consent will be done in person with added precautions. At UTSW and UCSD, consent will be completed remotely or in person depending on current directives.

8.1.1 CAMH – Informed Consent

Participants will be consented in person by appropriately trained and qualified CAMH research personnel who do not have an existing clinical relationship with the participant. Participant informed consent will be obtained for initial and ongoing participation.

Informed consent will be obtained prior to sending teleconferencing/videoconferencing information (such as links or access information) to participants and prior to the start of any remote session.

Participants must come into the hospital for blood work/ECG and an anesthesia consult as part of the clinical process for receiving treatment and confirmation of study eligibility. The research personnel will obtain consent when the participant is onsite for one of those appointments. The participant will be sent the Informed Consent Form (via email) ahead of that appointment so that they can read it ahead of time in order to minimize contact between the research personnel and the participant.

8.1.2 UTSW – Informed Consent

Participants will be given the option of face to face informed consent (if they are already attending UTSW for an ECT consult visit), or via remote consent if they have adequate access to technology. In both instances, the informed consent discussion will be conducted as usual, although if consent is remote this will occur in a telehealth visit. The Informed Consent Form (ICF) will then be signed either in person, or using a DocuSign format, ensuring a secure consenting process which is compliant with all FDA requirements.

8.1.3 UCSD – Informed Consent

Participants will be given the option of face to face informed consent conducted at the beginning of the screening visit, or via remote consent if they have adequate access to technology. In both instances, the informed consent discussion will be conducted as usual, although if consent is remote this will occur in a telehealth visit. The Informed Consent Form (ICF) will then be signed either in person, or using a DocuSign format, ensuring a secure consenting process which is compliant with all FDA requirements. The participant will be sent the Informed Consent Form (via email) ahead of their consent appointment so that they can read it ahead of time, and to minimize contact between the research personnel and the participant in the case of in-person consenting.

8.2 Study Assessments

All assessments listed in the protocol under Section 5.1.5 will be completed remotely via telemedicine. This includes assessments administered at screening, baseline, during treatment (e.g. post Tx 3, 6, 9, 12, 15, 18), post-acute treatment and 6-month follow-up visits (see updated Table 1: Schedule of Events in Appendix A).

Videoconferencing is preferred, as some of our assessments require scoring based on behavioral observation. If the participant has no access to videoconferencing during treatment, the procedures will be completed via telephone. Screening, baseline, post-acute treatment, and 6-month follow-up will only be completed by video. Both videoconferencing and telephone calls will not be recorded, however, we will use screen capture to for the image and clock drawing in the MoCA without capturing the participants face.

Due to certain limitations around the delivery of remote data collection, there will be certain assessments that cannot be covered virtually or will require an element of modification (i.e., self-report questionnaires and the MoCA) Clinical and cognitive measures are detailed below:

8.2.1 Clinical Assessment Battery

The following clinical rater-administered assessments will be completed virtually via videoconferencing: 1) Mini-International Neuropsychiatric Interview (M.I.N.I.), 2) Hamilton Rating Scale for Depression-24 (HRSD-24), 3) Scale for Suicidal Ideation (SSI), 4) Young Mania Rating Scale (YMRS), 5) Columbia ECT Subjective Side Effects Schedule, 6) the Clinical Global Impression Scale (CGI), 7) Demographics Form, 8) Medical History Form, 9) TMS Adult Safety Screen (TASS), and 10) Antidepressant Treatment History Form (ATHF).

The following self-report questionnaires will be completed virtually via videoconferencing or telephone call: 1) Brief Symptom Inventory (BSI) and 2) Quality of Life Enjoyment and Satisfaction Questionnaire (Q-LES-Q). For self-report questionnaires, the study personnel will complete the questionnaires by either reading the questions and answers verbatim to the participant and documenting their answers, or by virtually sharing their screen so that the participant can read the questions and provide the answers.

We are able to deliver the entire clinical assessment battery remotely via video call and this will be the medium of choice. If however participants do not have access to a camera, we will offer assessments via telephone during the acute treatment phase. In the case of telephone assessments during the acute treatment phase, we are unable to complete two items on the HRSD-24 which pertain to visual assessment of psychomotor retardation and agitation (Items 8 and 9). We will therefore plan to score these items as “0”, and will approach the assessments in the same fashion as the PRIDE study, which similarly used a telephone method of delivery for the HRSD-24[108, 109]. We will also be unable to assess appearance (Item 10) in the YMRS via telephone consult. We will plan to score this item as “0”, and as the YMRS is not a primary outcome this will have minimal impact on overall data integrity. In addition, the clinical rater will document that all of the above items could not be assessed for tracking purposes.

There is robust evidence around the effective delivery of virtual clinical measures [110, 111], and with the oversight and training provided by our clinical assessment lead, we are confident that data integrity will not suffer due to the remote collection of these assessments. In-person and remote assessments will be included as factors in the data analysis to confirm this. Raters will receive training on both in-person and virtual assessment administration. The clinical lead will be available throughout the study to provide ongoing support as needed.

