5.0 APPROACH

5.1.1 Research Design and Methods

The trial will be registered in an international clinical trial registry (clinicaltrials.gov) and results will be reported in a manner consistent with the international CONSORT guidelines. The study will involve a randomized, double blind, parallel-group clinical trial with two treatment arms conducted at three leading academic institutions in North America: CAMH, University of Texas Southwestern in Dallas, and University of California, San Diego (UCSD). Based on our power analysis (Section 5.7.1), a total of 260 participants with depression will be randomized to receive MST or RUL-UB-ECT. We plan to enroll four to five participants per month across the three study sites over 54 months.

Treatment will be administered two to three days per week. Depression symptoms will be assessed with the 24-item Hamilton Depression Rating Scale (HRSD-24) [74] and suicidality will be assessed with the Scale for Suicidal Ideation (SSI) [69]. Remission will be defined as HRSD-24 ≤ 10 and a $> 60\%$ decrease in scores from baseline on two consecutive ratings. Once a participant reaches remission, a second rating to confirm remission will be conducted immediately before their next scheduled treatment. If remission is confirmed, they will then be considered a completer of the acute treatment course. Remission of suicidal ideation is defined as a score of 0 on the SSI. Therefore, there will be no specific minimum number of treatments that patients must receive to be classified as remitters. However, patients who do not meet remission criteria after 21 treatment sessions will be considered non-remitters and will cease treatment sessions. This maximum treatment number was chosen allowing for the possibility that MST may require more treatment sessions to achieve remission, similar to RUL-UB ECT [29-31]. The blind will not be broken to participants until the completion of the entire study. Following completion of the acute treatment course, participants who achieve response (defined as a 50% reduction in symptoms on the HRSD-24 from baseline) or remission will be referred to a maintenance treatment trial.

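### Scoring the two unseen HRSD-24 items as 0 on telephone ratings, against a video baseline that scores them, makes the primary remission criteria easier to meet and pulls the comparison modestly towards non-inferiority

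*Combined protocol and SAP*

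**What the plan says.** Section 5.1.1 reads the primary endpoint from the HRSD-24 total. It begins "Remission will be defined as HRSD-24 ≤ 10 and a" and adds a fall of more than 60%, as a "decrease in scores from baseline on two consecutive ratings". The confirming rating is timed but its mode is not fixed: "a second rating to confirm remission will be conducted immediately before their next scheduled treatment".

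Section 8.2 sets the mode under the remote procedures. For the fixed visits, "Screening, baseline, post-acute treatment, and 6-month follow-up will only be completed by video". During the acute phase, "If the participant has no access to videoconferencing during treatment, the procedures will be completed via telephone".

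Section 8.2.1 states the consequence of a telephone rating: "we are unable to complete two items on the HRSD-24 which pertain to visual assessment of psychomotor retardation and agitation (Items 8 and 9"). The scoring rule follows: "We will therefore plan to score these items as “0”, and will approach the assessments in the same fashion as the PRIDE study". As a record, "the clinical rater will document that all of the above items could not be assessed for tracking purposes".

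Section 8.2.1 also zeroes one YMRS item and expects little impact because the YMRS is not a primary outcome. Section 5.1.5 makes the HRSD-24 the primary outcome measure. The text after Section 8.2.1 adds assessment mode to the analysis as in-person versus remote. Section 5.8.1 makes the primary test an unadjusted one-sided Z-test against a 15-point margin.

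**The concern.** Zero is the best score an item can take, so an item nobody could observe is recorded as symptom-free. The pre-treatment total contains items 8 and 9 and the telephone total does not. The absolute and the relative criterion both become easier with no change in the patient.

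The reason given for tolerating a zero on the YMRS is not available for the primary outcome, and no prorating, imputation or telephone sensitivity analysis is specified. The mode factor does not help: telephone and video are both remote, and the deciding test is unadjusted.

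In a superiority trial, equal misclassification in both arms would mostly cost power. Here it shrinks a true deficit, which favours the claim under test. Stage 1 also opens the gate to the Stage 2 cognitive test. A false remission before treatment 8 additionally brings the participant into the primary completer set as a success, because Sections 5.7.1 and 5.8.1 define completers as 8 treatments or remission.

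**Working it through.** **Inputs from the documents.** ECT remission 50%, margin 15 points (MST 35%), significance level 0.05, 130 per arm, 80% power (Section 5.7.1); one-sided Z-test (Section 5.8.1); baseline of at least 21 (Section 5.1.2); remission rule (Section 5.1.1).

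**The plan's own figure.** n per arm = V × (1.645 + 0.842)² / 0.15².
- Variance at 50% and 35%: V = 0.25 + 0.2275 = 0.4775. This gives 132 per arm (264 in total), and power at 130 of 79.7%.
- Variance at 50% in both arms: V = 0.50. This gives 138 per arm, and power at 130 of 78.0%.

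The stated 260 is reproduced, within rounding, at one-sided 0.05 with the first variance. The steps below use that set-up.

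**How many hidden points matter.** The highest recorded total that meets both criteria is:

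| Baseline | Highest qualifying total |
|---|---|
| 21–22 | 8 |
| 23–25 | 9 |
| 26 or more | 10 |

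- Baseline 21, telephone total 8: (21 - 8)/21 = 61.9%, remission. With one hidden point: (21 - 9)/21 = 57.1%, not remission.
- Baseline 26 or more, telephone total 10: remission. With one hidden point: 11, not remission.
- Zeroing items that scored 2 points at a baseline of 21 produces 2/21 = 9.5 percentage points of apparent improvement.

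**Effect on the comparison.** If a fraction f of true non-remitters is recorded as remitted, the observed rate is p + f(1 - p). With the same f in both arms, the observed difference is (1 - f) × the true difference. At the margin (50% versus 35%), with observed difference d and its unpooled standard error SE, type I error = Φ((0.15 - d)/SE - 1.645).

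| f, all participants | Observed rates | d | Type I error |
|---|---|---|---|
| 0 | 0.500, 0.350 | 0.150 | 0.050 |
| 1.5% | 0.508, 0.360 | 0.148 | 0.054 |
| 5% | 0.525, 0.383 | 0.1425 | 0.064 |
| 10% | 0.550, 0.415 | 0.135 | 0.081 |

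**What f might be (assumed, not in the documents).** Overall f is the telephone share times the fraction of telephone-rated non-remitters reclassified. A simulation with baseline mean 30 (SD 6, minimum 21) and on-treatment mean 13 (SD 8), using one rating, gives 36.2% remission. Hiding 1, 2 or 3 points from everyone adds 4.8, 9.7 or 14.7 points. At 2 points, f among telephone-rated participants is 0.097/0.638 = 15%. With a 10% telephone share, overall f = 0.10 × 0.15 = 1.5%, and type I error is 0.054. With a 30% share and 20% reclassified, f = 6% and the error is 0.067.

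**If the arms differed.** False remission in 5% of MST non-remitters only gives 0.133; in 5% of ECT non-remitters only, 0.020.

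**The case against.** Exposure is narrow. Telephone is a fallback for lack of video access, in the acute phase only, within the COVID-19 procedures. Anyone on that pathway needed video at screening and baseline and needs it again post-acute, so telephone use may be intermittent. This stands, and it is why the overall effect is probably modest.

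A reader might infer that the remission rate is inflated by about 10 points. The documents do not support that. The figure holds only among telephone-rated participants, assumes each hides 2 points, and uses a single rating. With two ratings correlated 0.8 (assumed), the 2-point case adds about 9 points if both are by telephone and about 4 if the second is by video.

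A reader might also infer that both qualifying ratings will be by telephone. The text permits it but does not establish it. Section 5.1.5 places a rating within four days of the last session, Section 8.2 makes the post-acute rating video-only, and Section 5.1.1 puts the confirming rating before the next scheduled treatment. These could be the same visit; the sections do not say.

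A third tempting reading is that the rule favours MST specifically. Nothing shows that telephone use or residual retardation and agitation differs by arm.

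Carrying forward the last observed item scores is not a clean repair either. Those scores may be pre-treatment, which creates false non-remission and also shrinks the difference: if 10% of remitters in each arm are lost, 15 points becomes 13.5 and type I error is 0.082.

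The cited earlier ECT trial is a precedent for the method, but its comparability cannot be checked from these documents.

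**Conclusion.** The point holds. Section 8.2.1 prescribes a scoring rule whose error runs in one direction, on the primary endpoint, against a baseline scored differently, and one hidden point at the threshold is enough to record a false remission. Neither the tracking note nor the in-person/remote factor removes it.

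The effect is likely modest: type I error of about 0.054 at an overall f of 1.5%, rising to 0.064 at 5% and 0.081 at 10%. These values assume equal f in both arms, true rates of 50% and 35%, and 130 per arm; the telephone share and residual item scores are unknown. Misclassification shared by both arms is sufficient for the drift towards non-inferiority. Differential bias remains a possibility only. The reason to act is that the rule is written into the plan, favours the hypothesis, and is cheap to replace before unblinding.

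**What to change.** Apply these changes to the analysed endpoint only, leaving treatment decisions as they are.

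1. **Scoring.** Do not enter 0 for unobserved items. For a telephone rating, compute the percentage criterion from the same 22 items at baseline and follow-up. For the 10-point criterion, prorate the 22-item total by 24/22 (9 becomes 9.8 and qualifies; 10 becomes 10.9 and does not). Do not carry forward pre-treatment item scores.
2. **Which rating counts.** Reconcile Sections 5.1.1, 5.1.5 and 8.2 on the rating that fixes the endpoint. Require at least one full 24-item rating, by video or in person, among those that determine analysed remission. The video post-acute rating already scheduled should be eligible, so no visit is added.
3. **Analysis.** Split telephone from video in the mode factor. Add two sensitivity analyses: multiple imputation of items 8 and 9, and telephone-only remitters counted as non-remitters. State that the second is not automatically conservative, since false non-remission also shrinks the difference. Report the telephone share by arm.

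The cost is SAP wording, rescoring of ratings already held, a little more analysis, and perhaps a slightly lower reported remission rate. Rescoring cannot recover what further treatment would have shown in participants whose acute course has already ended.
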